### 8.3 Sample Size

Several of the agents being utilized in the melanoma armamentarium have been evaluated in the neoadjuvant context including: HDI (Moschos et al. 2006), ipilimumab (Tarihini et al. 2014), pembrolizumab (Forde et al. 2018) and nivolumab/ipilimumab combination (Blank et al. 2018; Amaria et al. 2018). In earlier studies, response was typically assessed using chemotherapy criteria and reported as pathologic complete response (pCR) rates. Cognizant of the different mechanism of action of immuno-oncologic agents, more recent studies have utilized alternative means of assessing response using novel immuno-oncologic agent-specific criteria (major pathologic response or MPR rate) as delineated in **Section 8.4.** In the latter studies, MPR rates reported with PD-1 inhibitors range from 28% (Nivolumab, melanoma) to 45% (Nivolumab/Ipilimumab, melanoma) (Huang et al. 2019; Blank et al. 2018; Amaria et al. 2018).

However, the PD-1/CMP-001 combination has not been evaluated in the neoadjuvant setting and the MPR rate for this combination is unknown. To balance efficacy while minimizing exposure of patients to a potentially ineffective combination, we utilize Simon's minimax two-stage design with MPR as the primary endpoint.

In this study, we will test the null hypothesis of 28% MPR versus the alternative hypothesis of 55% MPR. In the 1st stage, we will enroll 14 evaluable patients (defined in **Section 5.8**). If we see at least 5/14 major pathologic responses, we will enroll a further 16 patients to the 2nd stage. The combination will be considered worthy of further evaluation if ≥13 responses are observed in both stages in 30 evaluable patients. The Simon's **minimax** two-stage design and sample size of 30 evaluable patients provides a type I error rate of 5%, with a power of 0.91. Allowing for 10% drop out rate, we set a total sample size of 33 patients.

#### 8.4 Efficacy Analysis

##### Definition of evaluable patient

See **Section 5.8**.

##### Determination of residual volume of tumor (RVT)

Early neoadjuvant studies in melanoma reported pCR utilizing criteria to define the residual volume of tumor (RVT) derived from neoadjuvant studies of chemotherapy in select tumors including lung cancer (Hellmann et al. 2014)

Neoadjuvant use of immuno-oncologic agents results in distinct histopathologic features compared to neoadjuvant chemotherapy. Specifically, neoadjuvant PD-1 therapy produces unusual features beyond CD8+ T cell infiltrate and tumor necrosis previously associated with response (Tumeh et al. 2014) including features in areas adjacent to the actual tumor – a location termed “the regression bed”. Histopathologic features associated with response herein include neovascularization; proliferative fibrosis; presence of cholesterol clefts; development of tertiary lymphoid structures; presence of plasma cells, giant cells, foamy macrophages and granulomas (Cottrell et al. 2018; Tetzlaff et al. 2018).

This observations have led investigators to propose new criteria – immune related pathologic response criteria (irPRC) – wherein immune related RVT (% irRVT) is defined as the total surface area of RVT divided by the total tumor bed area (comprising regression bed area + RVT area + areas of necrosis) (Cottrell et al. 2018; Tetzlaff et al. 2018). Compared to standard methods, irPRC had lower inter-observer variability better correlated with imaging assessments. The neoadjuvant administration of PD-1 and/or CTLA-4 inhibitors is associated with high PRR; ranging from 25-30% pCR (nivolumab monotherapy) to 45% pCR (ipilimumab/nivolumab combination) (Amaria et al. 2018; Blank et al. 2018). Primary endpoint of this study is MPR rate, where MPR is defined as ≤10% RVT remaining in post-therapy specimen using immunotherapy-specific criteria based on residual volume of tumor (RVT) (Cottrell et al. 2018; Tetzlaff et al. 2018).

Residual tumor will be determined in each resection specimen as outlined in **Appendix 2**. All tumors will be macroscopically localized after correlation with radiologic findings. Specimens were sectioned in 5 mm-thick slices. In patients with multiple metastases, each lesion will be extensively sampled from the center to the periphery to include multiple sections of tumor and non-neoplastic parenchyma. Sampling of the tumor nodules in the pathology suite will be directed at the most viable section of the tumor nodule. More than one section per centimeter will be reviewed from each tumor nodule. The number of hematoxylin-eosin slides reviewed per tumor nodule will be at least four (range, 1 to 14 slides). Hematoxylin-eosin stained sections will be reviewed by two melanoma pathologists blinded with respect to clinical information and treatment regimen.

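### Section 8.4 directs sampling at the most viable part of each nodule and contradicts itself on slide counts, while MPR is a 10% cut on a ratio over the whole tumour bed

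*Combined protocol and SAP*

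**What the plan says.** Section 8.4 (Determination of residual volume of tumor) states that the immune-related %RVT "is defined as the total surface area of RVT divided by the total tumor bed area". The bed is made up of regression bed, residual tumour and necrosis. MPR, the primary endpoint, is a value of 10% or less.

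The sampling paragraph in the same section contains these instructions:

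- Specimens are cut into 5 mm slices, after the tumours have been located with the help of imaging.
- In patients with multiple metastases, each lesion is sampled widely from centre to periphery, including non-neoplastic tissue.
- "Sampling of the tumor nodules in the pathology suite will be directed at the most viable section of the tumor nodule".
- Each nodule is reviewed at a density above one section per cm.
- The number of slides per nodule "will be at least four (range, 1 to 14 slides").

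Appendix 2 records the size of the tumour bed and the percentages of viable tumour, stromal fibrosis, necrosis and melanosis.

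Section 8.3 builds the decision rule on MPR: "we will test the null hypothesis of 28% MPR versus the alternative hypothesis of 55% MPR".

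**The concern.** A ratio over the whole bed has to be estimated from sections that represent the whole bed. Sections chosen because they hold the most viable tumour favour the numerator and under-represent regression bed and necrosis. For illustration, take a bed with 8% residual tumour. If viable tumour is over-represented 1.5-fold on the scored slides, it reads 1.5 × 8% = 12%, and the patient moves from MPR to non-MPR.

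The slide count does not settle the matter. A floor of four and a range that starts at one cannot both be prospective rules.

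The decision thresholds are small counts (5 of 14, then 13 of 30), so a few reclassified patients can change the result. A combination that meets the 55% target could be dropped because of how the slides were chosen.

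**Working it through.** **Step 1: which instructions fix where the scored sections come from?**

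| Text | What it fixes | What it leaves open |
|---|---|---|
| 5 mm slices | How the specimen is cut | Which slices are scored |
| Above one section per cm | Density, for every nodule | Location; it could be met inside the viable area |
| Centre-to-periphery sampling | Location | Applies only to patients with multiple metastases |
| Most viable section | Location, for nodules in general | How it combines with the broader sampling |
| Appendix 2 fields | Components to record | Which slides give the percentages |

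Patients with one lesion can enrol: section 5.1.2 admits single-site nodal disease from an unknown primary, and section 5.2.2.3 provides for a single accessible tumour. For them, the only instruction on location within the nodule is the viable-directed one. For patients with several lesions, both location instructions apply, and nothing says how the sections combine into one %RVT.

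**Step 2: reproduce the plan's design figures.** Inputs from section 8.3:

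- Stage 1: "If we see at least 5/14 major pathologic responses, we will enroll a further 16 patients".
- Final rule: "The combination will be considered worthy of further evaluation if ≥13 responses are observed in both stages in 30 evaluable patients".
- Claimed: the design "provides a type I error rate of 5%, with a power of 0.91".

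The exact probability of declaring success at an observed MPR rate p is

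P(p) = Σ (x = 5 to 14) C(14, x) p^x (1 − p)^(14 − x) × Pr[Bin(16, p) ≥ 13 − x].

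- P(0.55) = 0.907, against the stated 0.91.
- P(0.28) = 0.047, against the stated 5%; the exact value is lower because counts are discrete.

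The design figures reproduce and are not in dispute.

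**Step 3: sensitivity to viable-directed scoring.** The documents give no misclassification rate. Assume that a fraction f of true MPRs is read above 10% RVT, that no true non-MPR is read as MPR, and that f is the same under both hypotheses. The observed rate is then p × (1 − f).

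| f (assumed) | Observed rate if true rate is 55% | Power | Chance of stopping at stage 1 (true 55%) | Observed rate if true rate is 28% | Type I error |
|---|---|---|---|---|---|
| 0 | 55.0% | 0.907 | 4.3% | 28.0% | 4.7% |
| 5% | 0.55 × 0.95 = 52.3% | 0.850 | 6.5% | 26.6% | 3.2% |
| 10% | 0.55 × 0.90 = 49.5% | 0.773 | 9.6% | 25.2% | 2.1% |
| 20% | 0.55 × 0.80 = 44.0% | 0.566 | 18.7% | 22.4% | 0.8% |

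**The case against.** The best defence reads the paragraph as a whole. Slicing, section density and wide sampling come first, and the viable-section sentence is a safeguard so that residual tumour is not missed. Appendix 2 already collects the size of the bed and its components. Any error from the sentence makes a success harder to declare. The documents also do not say how nodules were sampled in the study behind the 28% benchmark. If it used similar sampling, removing the instruction altogether could reduce comparability.

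Much of this stands. The safeguard reading is plausible, the direction is conservative, and the benchmark point argues against simple deletion. But the text does not call the viable-directed sections an addition, and step 1 shows that the other rules do not supply the missing location rule for a single lesion.

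Two stronger readings go beyond the documents:

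- A reader might infer that %RVT and the MPR rate are certainly biased. The text shows only that the rules are inconsistent and leave room for bias; pathologists may in practice score the whole bed.
- A reader might take the sentence to mean that viable tissue is removed for research first, so that the remaining slides under-represent tumour and false positives rise. Banking is mentioned in section 5.10 and Appendix 2, but nothing says that it precedes scoring, and the sentence sits among the instructions for response assessment.

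**Conclusion.** The concern holds as a conflict between the sampling wording and the definition of the primary endpoint, together with a slide count that contradicts itself. If scoring uses viable-directed sections, the likely effect is to overstate %RVT and understate MPR; the size is unknown. Under assumed losses of 5% to 20% of true MPRs, power lies between 0.850 and 0.566 instead of 0.907, while type I error falls below its planned level. The practical risk is therefore that an active combination is missed. These figures rest on one-directional misclassification at assumed rates and are a sensitivity range, not an estimate for this trial. The design calculation in section 8.3 is unaffected.

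**What to change.** In section 8.4 and Appendix 2:

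1. State that %RVT is scored on slides representing the whole tumour bed (regression bed, viable tumour and necrosis) for every lesion, including single lesions.
2. Keep sampling of the most viable area only as a supplement, so that residual tumour is not missed. One sentence on how the sections combine into the patient's %RVT would complete the rule.
3. Delete the parenthetical range of 1 to 14 and keep the minimum of four slides per nodule, with a stated exception for lesions too small to yield four.

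The cost is minor wording work with the pathologists and the small-lesion exception. No extra reader or procedure is needed, and the sample size and decision rule do not change.

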##### Definition of major pathologic response (MPR)

MPR is defined as ≤10% RVT remaining in post-therapy specimen using immunotherapy-specific pathologic response criteria (irRPRC) (Cottrell et al. 2018; Tetzlaff et al. 2018). MPR rate will be

calculated along with its exact 95% confidence interval. Other categories of response based on %RVT are given below:

- Pathologic complete response (pCR): 0% RVT
- Major pathologic response (irMPR): ≤10% RVT
- Partial pathologic response: <10% but ≤50% RVT
- Pathologic non-response: >50% RVT.

#### Definition of other endpoints

RFS is defined as the time from initiation of treatment till melanoma relapse or death. All suspected relapse should be biopsied to confirm relapse. In the event where this is difficult and/or dangerous, imaging may be used as a surrogate. OS is defined as the time from initiation of treatment till death. Kaplan-Meier estimates of RFS and OS will be provided. The corresponding median survival time (with 95% confidence intervals) will be determined, along with survival estimates at selected time points (e.g. 6 months, 1 years, and 2 years).

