## **5.2 Trial Treatments**

This is a neoadjuvant biotherapy study testing nivolumab with CMP-001 in patients with locally/regionally advanced/recurrent melanoma. Subjects will receive combination nivolumab/CMP-001 for 7 weeks (Prime Phase) prior to surgery. Surgery will be scheduled approximately 2 – 4 weeks after completion of Prime Phase depending on recovery. After recovery from surgery subjects will receive additional nivolumab/CMP-001 for approximately 46 additional weeks of study drug(s)

administration (Boost Phase). The treatment to be used in this trial is outlined below. Trial treatment should begin within 4 weeks of study registration.

[figure not shown]

Figure 2: Trial Diagram

Allocation of study treatment arm: Up to 40 evaluable patients will be enrolled to receive nivolumab/CMP-001 combination.

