### **5.8 Subject Replacement Strategy**

Subjects who receive at least 1 dose of CMP-001 and nivolumab are evaluable for safety. Patients who complete pre-operative therapy and receive surgery will be evaluable for pathologic response rate and other efficacy endpoints. Patients who did not undergo surgery for reasons of disease progression precluding surgery (rapid disease progression) will be deemed non-evaluable. Non-evaluable subjects may be replaced.

If in the opinion of the treating investigator and treating surgical oncologist in consultation with Principle Investigator, subject's disease is rapidly progressing to the point that window to intervene surgically is narrowing, treatment may be discontinued to permit surgery. These patients are evaluable for pathological response rate and other efficacy endpoints. These patients are eligible to receive CMP-001/nivolumab during "Boost" phase.

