## 8 Statistical Analysis Plan

### 8.1 Study Design

This is a non-randomized phase II single arm Simon's minimax two-stage study of neoadjuvant nivolumab and CMP-001. Nivolumab (I.V.) and CMP-001 (intra-tumorally) will be administered for 7 weeks pre-operatively (weeks 1-7) followed by planned surgical resection at week 8-10. Following recovery from surgery, nivolumab (I.V.) and CMP-001 (S.C. or peri-tumoral resection site) will commence and continue for 48 weeks. Details for the two-stage design are in **Section 8.3**.

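### RFS and OS run from first dose, but the only population rule points to patients who reach surgery, and RFS has no clear event for patients never resected

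*Combined protocol and SAP*

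**What the plan says.** Section 8.4, under the definition of other endpoints, gives two time-to-event definitions: "RFS is defined as the time from initiation of treatment till melanoma relapse or death" and "OS is defined as the time from initiation of treatment till death". It asks for suspected relapse to be confirmed by biopsy, with imaging as a substitute where biopsy is difficult or dangerous. It plans Kaplan-Meier curves, medians, and estimates at times such as 6 months, 1 year and 2 years. The paragraph names no analysis set.

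The only population text in 8.4 is the short item headed "Definition of evaluable patient", which sends the reader to Section 5.8. Section 5.8 contains three relevant rules:

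- The general rule for the efficacy set is: "Patients who complete pre-operative therapy and receive surgery will be evaluable for pathologic response rate and other efficacy endpoints".
- A separate rule takes out those whose disease has become unresectable: "Patients who did not undergo surgery for reasons of disease progression precluding surgery (rapid disease progression) will be deemed non-evaluable". Such patients may be replaced.
- Of patients whose treatment is cut short so that surgery is still possible, it says: "These patients are evaluable for pathological response rate and other efficacy endpoints".

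Sections 5.7 and 7.1.7.5 provide for survival follow-up of all subjects, including those who progress. Section 3.2 lists RFS and OS as secondary objectives, with the hypothesis that the combination improves both.

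**The concern.** A time-to-event estimate that starts at first dose should include everyone who received a first dose. If membership of the set is decided weeks later by whether surgery took place, nobody in the set can have died before surgery, and patients who became unresectable through progression are removed. Those are likely to be among the worst early outcomes, and Section 5.8 allows them to be replaced by patients who do reach surgery. The 6-month, 1-year and 2-year figures would still be read as results from the start of treatment.

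The second problem is the RFS event. Patients carry measurable tumour at entry. For a patient who is never resected, relapse has no clear meaning, because there was no disease-free state to relapse from. If the set were widened to all treated patients and nothing else changed, a living patient with unresectable progression could be counted as relapse-free.

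The same endpoints feed the Cox biomarker models in Section 8.6, so both gaps carry over to those analyses.

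**Working it through.** **Nothing to reproduce for RFS or OS.** The documents give no assumed or target rate for either. The primary-endpoint design in Section 8.3 (at least 5/14, then at least 13/30, 28% against 55%) was recomputed with exact binomial sums. Type I error is 0.047 and power 0.907, against the stated 5% and 0.91. Those figures concern major pathologic response and do not depend on this point.

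**When set membership is decided.** Section 8.1 has treatment in weeks 1 to 7 "followed by planned surgical resection at week 8-10". Section 5.2 puts surgery about 2 to 4 "weeks after completion of Prime Phase depending on recovery", that is 7 + 2 = 9 to 7 + 4 = 11. Together these give about weeks 8 to 11. For a 6-month (26-week) estimate, 8/26 = 31% to 11/26 = 42% of the interval lies before the qualifying event. The share is less for patients taken to surgery early.

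**Illustration of the population effect.** These inputs are assumptions: 30 evaluable patients (the number in 8.3), k further treated patients excluded for progression before surgery, and 12-month status known for all, so that each estimate is a simple proportion. Reported RFS is taken as 24/30 = 80.0% and reported OS as 27/30 = 90.0%.

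All-treated RFS with each excluded progressor an event = 24/(30 + k). All-treated OS with none of the excluded alive = 27/(30 + k).

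| k | RFS | Overstatement | OS | Overstatement |
|---|---|---|---|---|
| 1 | 24/31 = 77.4% | 2.6 points | 27/31 = 87.1% | 2.9 points |
| 2 | 24/32 = 75.0% | 5.0 points | 27/32 = 84.4% | 5.6 points |
| 3 | 24/33 = 72.7% | 7.3 points | 27/33 = 81.8% | 8.2 points |

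The OS columns are the worst case. If half of the excluded are alive (an expected count), OS is 27.5/31 = 88.7% to 28.5/33 = 86.4%, an overstatement of 1.3 to 3.6 points. If all are alive, it is 28/31 = 90.3% to 30/33 = 90.9%, and the reported figure is 0.3 to 0.9 points too low. If every treated patient reaches surgery, k = 0 and there is no population effect.

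The value k = 3 equals the dropout allowance (33 − 30) but is not a ceiling. Section 5.8 sets no limit on replacement, and Section 5.2 allows up to 40 evaluable patients. With k = 5, RFS would be 24/35 = 68.6%, an overstatement of 11.4 points.

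**Illustration of the event gap.** Suppose RFS is analysed in all treated patients and the k unresected progressors are alive at 12 months. Counting them as relapse-free gives (24 + k)/(30 + k); counting them as events gives 24/(30 + k). The gap is k/(30 + k).

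- k = 1: 25/31 = 80.6% against 24/31 = 77.4%, a gap of 3.2 points.
- k = 3: 27/33 = 81.8% against 24/33 = 72.7%, a gap of 9.1 points.

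Naming the population without defining the event would therefore not settle the estimate.

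**The case against.** The strongest reply is that the restriction is not stated where RFS and OS are defined. Both clocks start at first dose, all subjects are followed for survival, and Section 8.3 uses evaluability only to count patients for the response rule. An all-treated analysis, above all for OS, is an arguable reading. This stands in part: the restriction is the plain reading of 8.4 with 5.8, not an express one. But the follow-up sections govern data collection and do not define an analysis set, and 5.8 extends evaluability beyond pathologic response in terms.

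A reader might also infer that any progression on the pre-surgical scan leaves the RFS event open, even when the disease is then resected. The documents do not support that. Section 8.4 wants suspected relapse biopsied, and the protocol keeps progression and recurrence apart as terms. A RECIST increase in known tumour that is then removed is not naturally a relapse. One confirming sentence is enough there; the real gap is the never-resected patient.

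Nor are patients who miss surgery through toxicity or refusal left unclassified. They fail the 5.8 definition of evaluable; what is missing is an explicit replacement rule for them.

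Finally, the effect may be small. Potential resectability is required at entry, early surgery is allowed, and the illustrated shifts lie inside the exact 95% intervals (61% to 92% for 24/30, 73% to 98% for 27/30). That limits the consequence. It does not justify a systematic exclusion that a wording change can remove.

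**Conclusion.** The point holds. Followed as most naturally read, the plan estimates RFS and OS from first dose in patients selected by a later event, and leaves out treated patients who became unresectable. The estimates are too favourable to the extent that those patients do worse. Separately, the RFS definition does not work for patients who are never resected.

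The size cannot be established from the documents. The 2.6 to 7.3 points for 12-month RFS rest on an assumed 24/30, on 1 to 3 exclusions, and on counting each exclusion as an event. OS could move in either direction, depending on how the excluded patients fare.

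These are secondary, descriptive estimates. A reader might infer that the trial's decision rule is compromised by this point; it is not, since no test, alpha or power depends on RFS or OS. The change should be made before these endpoints are analysed.

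**What to change.** 1. In Section 5.8, limit surgery-based evaluability to pathologic response.
2. In Section 8.4, name all patients who received study treatment as the set for OS and RFS (or an event-free endpoint in place of RFS), with time from first dose.
3. List the RFS events: progression that precludes surgery; progression in patients not resected for any other reason; relapse after surgery; death from any cause.
4. State that progression before a completed resection is not itself an event. This suits Section 5.2.2.8, which warns that inflammation of an injected tumour can be mistaken for progression.
5. If a resected-only RFS is kept, start it at completion of definitive surgery (Section 5.10 allows staged procedures) and label it as conditional on resection.
6. Record the date of the change relative to data already seen; the protocol is at version 11, so this needs saying.

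The cost is wording in two sections. Survival follow-up (5.7, 7.1.7.5), the pre-surgical scan (7.1.3.6) and imaging after stopping treatment for reasons other than progression (7.1.7.4) are already planned. The downside is that the reported estimates may be a few points lower.
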